2.2.4. Engensis and VM202

The investigational agent (study drug) being studied in this protocol is Engensis, which contains the active pharmaceutical ingredient VM202. VM202 is a plasmid DNA that contains the novel genomic complementary DNA (cDNA) hybrid human HGF coding sequence (HGF-X7) expressing two isoforms of HGF, HGF₇₂₈ and HGF₇₂₃ (Figure 2).

proteins.

[figure not shown]

Figure 2: VM202 Construct

2.2.5. Nonclinical Data

The nonclinical safety of Engensis has been evaluated for general toxicity following single IM and intravenous doses in rats (up to 28 days) and following multiple intermittent (weekly or monthly) IM doses in rabbits and rats (up to 8 weeks; see the IB). The potential for genomic integration at the injection site as well as the potential for distribution to and persistence of VM202 in reproductive tissues was evaluated in rats. The ability of VM202 to induce humoral immune responses was evaluated following IM administration with or without adjuvant in mice. All species used for these studies (mouse, rat, and rabbit) were shown in in vivo experiments to be able to express the plasmid following IM injection.

Collectively, Engensis has been well-tolerated in all preclinical studies conducted to date, with the only evidence of toxicity consisting of mild, transient injection site irritation. No evidence of systemic toxicity has been noted in any nonclinical study, and human HGF was not detected in the sera of rats or rabbits following intramuscular injection (assay lower limit of quantitation [LLOQ] of 125 pg/mL). No evidence has been seen of genomic integration, potential germ cell transmission, or immunostimulatory effects following IM administration of Engensis to animals.

2.2.6. Clinical Data

Engensis has been or is being evaluated in 10 clinical studies in the US and/or Korea. These include two studies (Phases 1 and 2) in critical limb ischemia (CLI), one study in peripheral

artery disease (Phase 2), one study in coronary artery disease (Phase 1), four studies (Phase 1/2, Phase 2, and two Phase 3) in Participants with painful diabetic peripheral neuropathy (DPN), a study (Phase 1/2) in ALS, and one (Phase 3) study in diabetic Participants with chronic nonhealing foot ulcers (NHU). Engensis was well tolerated and the most frequent reaction was pain at injection sites in 1-4% of Participants, which was similar to that observed in the placebo groups. No systemic effects have been attributed to Engensis.

2.2.6.1. Phase 1/2 Study in Participants with Amyotrophic Lateral Sclerosis

A Phase 1/2, open label, single center study in 18 Participants diagnosed with clinically definite, clinically probable, or clinically probable-laboratory supported ALS (VMALS-001; NCT02039401) lasting 9 months was completed.⁶¹ Prior to injections on Day 0, Participants were assessed using the ALSFRS-R, the Medical Research Council (MRC) scale for muscle strength testing, dynamometry, forced vital capacity (FVC), and muscle circumference of treated muscles.

All Participants (18 Participants) received a total of 64 mg of Engensis IM in the upper limbs (abductor pollicis brevis, first dorsal interosseous, biceps, deltoid, extensor carpi radialis, flexor carpi ulnaris, and flexor carpi radialis) and lower limbs (quadriceps, gastrocnemius, and tibialis anterior).

Engensis was administered over the course of four visits: Days 0, 7, 14, and 30. As in previous Engensis studies, the final dose of Engensis for each target muscle group was divided and administered 2 weeks apart with injection of the upper limbs at separate visits followed by injection of the lower limbs.

Post-injection, ALSFRS-R, FVC, and muscle strength (determined by the MRC scale) were assessed at Days 30, 60, and 90, and at 6 and 9 months. Muscle circumference and dynamometry were conducted on Days 60 and 90, and at 6 and 9 months. Participants were contacted through 36 months by phone to assess survival.

After Engensis or Placebo injections through Day 30, seventeen (17) Participants completed the 9-month follow-up; one Participant died prior to the 9-month visit. Three (3) Participants completed the study (36-month follow-up), while 14 Participants died following the 9-month visit; all deceased Participants died due to respiratory failure associated with ALS. Four additional serious adverse events (SAEs) that required hospitalization were reported. All deaths and SAEs were classified as unrelated to the study drug. Injection site reactions were limited to pain and/or bruising and none exceeded grade 2 severity.

2.2.6.2. Other Engensis Clinical Studies

See the IB for detailed presentation of results from all 10 clinical studies in the USA and Korea (see Section 2.2.6). Also, see Section 4.3 (Dose Justification) for descriptions of prior clinical studies with Engensis that contributed to the selection of doses and dosing regimen for this current study.

2.3. Benefit/Risk Assessment

2.3.1. Risk Assessment

The risks for the study medication and study procedures are summarized in the following table.

Potential Risk of Clinical Significance	Summary of Data/Rationale for Risk	Mitigation Strategy
Risks of Engensis		
Cancer Patients with melanoma and tongue cancer appear to be at an increased risk of death due to ALS⁶²	Angiogenesis plays an important role in the proliferation and metastatic spread of cancer as these processes are dependent on an adequate supply of oxygen and nutrients and removal of waste products.	Participants who develop any type of cancer during VMALS-002-2 will be followed long-term in VMALS-002-2b
Angiogenesis	Intimal angiogenesis in atherosclerotic plaques contributes to unstable plaque, plaque hemorrhage, and plaque rupture that predisposes to thrombotic or embolic events.	Participants who have experienced a stroke, cerebrovascular accident, or myocardial infarction within 3 months before Screening for VMALS-002-2 and Participants with peripheral artery disease (PAD) or PAD requiring revascularization will be excluded from VMALS-002-2b
Risks of Study Procedures		
Complications of venipuncture (for blood draws for laboratory tests)	Venipuncture complications include minor bruising, hypotension, and syncope.	Incidence of adverse events of bruising, hypotension, and syncope will be closely monitored throughout the study.

Adverse Events in Clinical Studies

Engensis has been well tolerated in all clinical studies conducted thus far in more than 500 Participants. The preponderant adverse events have consisted of mild, transient injection site effects, including itching, erythema, pain, and muscle spasms. Other TEAEs that have been reported were generally mild to moderate. Refer to the IB for a table of AEs that occurred in $\geq 2\%$ of trial Participants.

Five SAEs have been reported to date as possibly related to study treatment:

- Colon cancer in the Phase 1 trial of CLI (assessed by the investigator to be possibly related to study drug and, even though the sponsor noted that the Participant had a history of colon polyps, a relationship to study drug could not be ruled out)
- Peroneal deep vein thrombosis (categorized as possibly related to the study injection) in the Phase 2 trial of CLI. The mechanism by which HGF or VM202 could be causative is not established.

SAEs reported as possibly related in the VMDN-003 trial included:

- Vitreous hemorrhage of the eye (categorized as possibly related to the study drug but was probably related to underlying disease)
- Myocardial infarction (categorized by Helixmith as possibly related to the study drug, although categorized by the investigator as not related to the study drug)
- Adenocarcinoma (categorized as possibly related to the study drug by the investigator and not related to the study drug by Helixmith)

2.3.2. Benefit Assessment

In ALS, sustained, local production of HGF in neural tissue may alleviate symptoms by direct neurotrophic and indirect neuroprotective activities on motor neurons. HGF has also been reported to play an important role in reversing or limiting muscle damage and muscular atrophy; exogenous treatment of HGF ameliorated skeletal muscle atrophy and increased the generation of new muscle fibers.

Engensis induces relatively rapid and prolonged production of HGF, which, through its multiple mechanisms of actions on microvascular and neural tissue repair, has the potential to improve outcomes in ALS patients, as suggested by preceding studies. If Engensis shows favorable outcomes in this study, it may be considered an important agent with a durable therapeutic effect for ALS patients.

2.3.3. Overall Benefit / Risk Conclusions

The overall profile of potential benefits and apparent safety for Engensis provide sufficient support to justify the conduct of the present extension study in its aim to meet the unmet needs of ALS patients.

3. OBJECTIVES AND ENDPOINTS

Objectives and endpoints for this extension study are presented in the following table. Note that there will be no Engensis or Placebo treatments in VMALS-002-2b. Therefore, the comparisons of Engensis to Placebo for long-term safety in VMALS-002-2b are based on the randomization of Participants and the treatments they received in VMALS-002-2 (Engensis or Placebo).

Objectives	Endpoints
Primary	

 To evaluate the long-term safety of intramuscular (IM) injections of Engensis in Participants with Amyotrophic Lateral Sclerosis (ALS) 	
 Incidence of treatment-emergent adverse events (TEAEs), treatment-emergent serious adverse events (TESAEs), and adverse events of special interest (AESIs) for Engensis compared to Placebo Incidence of clinically significant laboratory values for Engensis compared to Placebo
Exploratory	

 To evaluate changes in muscle function following Engensis injections in ALS Participants 	
 Change from Baseline (Study VMALS-002-2 Day 0) in total mean Revised Amyotrophic Lateral Sclerosis Function Rating (ALSFRS-R) scores at Day 365 for Engensis compared to Placebo Change from Baseline (Study VMALS-002-2 Day 0) in ALSFRS-R subscores for Fine and Gross Motor Functions (sum of scores for items 4 to 9) and for Bulbar Function (sum of scores for items 1 to 3) at Day 365 for Engensis compared to Placebo Changes in the slope of the total ALSFRS-R score over time for Engensis compared to Placebo

Objectives	Endpoints

 To evaluate muscle strength changes following Engensis injections in ALS Participants 	
 Change from Baseline (Study VMALS-002-2 Day 0) in muscle strength assessed bilaterally by Handheld Dynamometry (HHD) in muscles in the upper and lower extremities at Day 365 for Engensis compared to Placebo

 To determine whether IM administration of Engensis has effects on respiratory function in ALS Participants 	
 Change from Baseline (Study VMALS-002-2 Day 0) in Slow Vital Capacity (SVC) at Day 365 for Engensis compared to Placebo Time to tracheostomy for Engensis

 To determine whether IM administration of Engensis has positive effects on survival in ALS Participants 	
 Time to all-cause mortality compared to Placebo

 To evaluate Quality of Life improvement following Engensis injections in ALS Participants compared to Placebo 	
 Change from Baseline (Day 0) in Quality of Life (QoL) using the ALS Assessment Questionnaire (ALSAQ; with 40 items, ALSAQ 40) on Day 365 for Engensis compared to Placebo

 To evaluate Patient and Clinical Reported Outcome improvement following Engensis injections in ALS Participants compared to Placebo 	
 Patient Global Impression of Change (PGIC) and Clinical Global Impression of Change (CGIC) at Day 365 for Engensis compared to Placebo

4. STUDY DESIGN**4.1. Overall Design**

VMALS-002-2b is a safety extension study following VMALS-002-2 (A Phase 2a, double-blind, randomized, placebo-controlled, multicenter study designed to assess the safety of IM administration of Engensis in Participants with ALS). Following completion of the Day 180 visit in VMALS-002-2 and signing of written informed consent, Participants may be enrolled in this approximately 180-day extension study.

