1.1. Synopsis

Protocol Title: A 6-Month Extension Study Following Protocol VMALS-002-2 (A Phase 2a, Double-Blind, Randomized, Placebo-Controlled, Multicenter Study to Assess the Safety of Engensis in Participants with Amyotrophic Lateral Sclerosis)

Short Title: A 6-Month Extension Study to Assess the Safety of Engensis in Amyotrophic Lateral Sclerosis

Rationale:

The purpose of this study is to evaluate the long-term safety of intramuscular (IM) administration of Engensis in Participants with Amyotrophic Lateral Sclerosis (ALS) who were previously randomized, received treatment, and completed the Day 180 Visit of Study VMALS-002-2. Safety will be assessed by incidences of treatment-emergent adverse events (TEAEs), treatment-emergent serious adverse events (TESAEs), adverse events of special interest (AESIs), and the clinically significant laboratory values. See the table below for additional, exploratory endpoints.

Engensis contains the active pharmaceutical ingredient VM202, a novel genomic complementary deoxyribonucleic acid (cDNA) hybrid human hepatocyte growth factor (HGF) coding sequence (HGF-X7) expressing two isoforms of HGF, HGF₇₂₈ and HGF₇₂₃, being developed by Helixmith for treatment of ALS.

Data from Helixmith's first clinical trial in ALS, the Phase 1/2 study (VMALS-001) that included 18 Participants who were followed for 9 months, suggested that targeted delivery of HGF to motor neurons via intramuscular (IM) injections of Engensis was safe and well-tolerated. Safety assessments during the study included reports of 79 adverse events (AEs) in 17 Participants (94.4%), including 26 mild injection site reactions (Grade 1). Five SAEs were reported in 3 Participants. Only an injection site reaction was considered related to study treatment. Following injections until Day 90, a plateau or a relative slowing in the decline of the Revised Amyotrophic Lateral Sclerosis Function Rating (ALSFRS-R) scores and muscle strength was noted, suggesting a slowing of disease progression. After 90 days, the plateau was no longer observed in the ALSFRS-R, with the notable exception of a trend toward better preservation of bulbar and breathing functions as measured by the ALSFRS-R.

Data for Participants at study visits in Study VMALS-002-2 will be used as reference points for changes in safety assessments during the extension study VMALS-002-2b.

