8.2. Other Assessments and Procedures

8.2.1. Revised Amyotrophic Lateral Sclerosis Functional Rating

The ALSFRS-R is a validated rating scale for measuring the global function of patients with ALS. It provides a health professional-generated estimate of the patient's degree of functional impairment, which can be evaluated serially to objectively assess any response to treatment or progression of disease. The ALSFRS-R includes twelve questions that ask the Investigator to rate his/her impression of the patient's level of functional impairment in performing one of twelve common tasks, e.g., climbing stairs. Each task is rated on a five-point scale from 0 (can't do) to 4 (normal ability). Individual item scores are summed to produce a reported score between 0=worst and 48=best. The ALSFRS-R will be conducted on Days 240, 300, and 365/ET. Details about the scale can be found in Section 10.4, Appendix 4.

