6.2.9 Revised Amyotrophic Lateral Sclerosis Functional Rating Scale (ALSFRS-R)

Subscore for Fine and Gross Motor Functions will be calculated as sum of scores for items 4 to 9; subscore for Bulbar Function will be calculated as sum of scores for items 1 to 3. Total score will be calculated as sum of scores for items 1 to 9.

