6.15 Exploratory Analyses

6.15.1 Revised Amyotrophic Lateral Sclerosis Functional Rating Scale (ALSFRS-R)

ALSFRS-R will be measured at Day 240, Day 300 and Day 365. Total score and subscores for Fine and Gross Motor Functions (sum of scores for items 4 to 9) and for Bulbar Function (sum of scores for items 1 to 3) their changes from baseline will be presented with descriptive statistics by visits and treatment group (Table 14.6.1, Listing 16.2.9.1).

Slope of the total score will be provided using graphical presentation of values by visit for both treatment group. The figures will be presented using time points from both VMALS-002-2 and VMALS-002-2b studies.

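### No ALSFRS-R breathing subscore (items 10 to 12) is planned and the SAP total also omits these items, so the VMALS-001 breathing trend cannot be described on the scale where it was reported

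*Protocol*

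**What the plan says.** **Background.** The rationale in Protocol 1.1 reports that the VMALS-001 plateau on the ALSFRS-R was no longer seen after 90 days, "with the notable exception of a trend toward better preservation of bulbar and breathing functions as measured by the ALSFRS-R".

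**Objectives and subscores.** Protocol 3 lists an exploratory objective on respiratory function, with change in SVC and time to tracheostomy as its endpoints. Under the separate muscle-function objective it lists "ALSFRS-R subscores for Fine and Gross Motor Functions (sum of scores for items 4 to 9) and for Bulbar Function" (the bulbar subscore being items 1 to 3). SAP 3.2, 6.2.9 and 6.15.1 repeat the same two subscores. No section of either document defines a subscore for items 10 to 12.

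**Total score.** Protocol 8.2.1 describes twelve items rated 0 to 4: "Individual item scores are summed to produce a reported score between 0=worst and 48=best". SAP 6.2.9 differs: "Total score will be calculated as sum of scores for items 1 to 9". SAP 9 declares no change from the planned protocol analysis.

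**Outputs.** SAP 6.15.1 gives descriptive statistics for "Total score and subscores for Fine and Gross Motor Functions (sum of scores for items 4 to 9) and for Bulbar Function" by visit and treatment group in Table 14.6.1, and a figure of the total over time. The scale is completed at Days 240, 300 and 365/ET, so items 10 to 12 are collected at every extension visit.

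**The concern.** The exception that the rationale singles out has two parts, bulbar and breathing. The plan summarises bulbar function and motor function, which is not part of the exception, and leaves breathing out. Neither document gives a reason.

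A reader would expect the total score to carry the breathing items at least in part. Under the SAP's derivation it does not, and neither does the slope figure built on that total. At stake is whether the clinical study report can show how breathing changed, by arm, on the scale that the sponsor cites. If this is not pre-specified, such a summary could still be added later as an additional analysis, which SAP 6 allows, but it would then be chosen after the data were seen.

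**Working it through.** **1. The plan's own figure.** Twelve items rated 0 to 4 (Protocol 8.2.1): 12 × 4 = 48. This reproduces the stated maximum.

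**2. The SAP total.** Items 1 to 9: 9 × 4 = 36.

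**3. What the planned scores cover.**
- Motor, items 4 to 9: 6 × 4 = 24 points
- Bulbar, items 1 to 3: 3 × 4 = 12 points
- Motor + bulbar: 24 + 12 = 36, which is exactly the SAP total
- Breathing, items 10 to 12: 3 × 4 = 12 points; 12/48 = 25% of the scale

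Under the SAP as written, a difference confined to items 10 to 12 adds zero to the total, to both subscores and to the slope figure. With a breathing subscore the parts add up to the protocol's scale: 24 + 12 + 12 = 48.

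**4. What the other respiratory endpoints capture.**
- SVC (SAP 6.15.5) is a lung volume. It does not record dyspnea, orthopnea or graded use of ventilatory support. VMALS-001 also measured vital capacity (as FVC, Protocol 2.2.6.1), but the synopsis attributes the trend to the ALSFRS-R.
- Time to tracheostomy (SAP 6.2.3) is the first ALSFRS-R with item 12 scored 0. It uses one of the three breathing items, at its floor. Changes in items 10 and 11, and in item 12 from 4 down to 1, do not count.
- Pulmonary events are adverse events of special interest (Protocol 8.3.4.2, SAP 6.14.1.3). They are event counts, not a functional score.

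**5. Would correcting the total be enough?** Illustration only, because the documents give no effect or SD. Assume a 1.5-point difference confined to breathing, a breathing-change SD of 2, and a total-change SD of 7 (range 5 to 9). The standardised difference is 1.5/2 = 0.75 on the subscore. On a twelve-item total it is 1.5/7 = 0.21 (1.5/5 = 0.30 down to 1.5/9 = 0.17). This dilution applies only after the total is corrected; on the nine-item total the contribution is zero.

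**6. What the subscore could show.** Assume SD 2 again, with all 18 participants evaluable; the allocation is not given. The half-width of a 95% interval for the difference between arms is t × SD × √(1/n₁ + 1/n₂), with t = 2.12 on 16 degrees of freedom.
- 9:9: 2.12 × 2 × √(2/9) = 2.0 points
- 12:6: 2.12 × 2 × √(1/12 + 1/6) = 2.1 points

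A 1.5-point difference would carry an interval of about −0.5 to 3.5 at 9:9. The half-width scales with the assumed SD, and attrition widens it.

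**The case against.** **The plan does examine respiratory function.** A reader might infer that breathing is never looked at. The documents do not support that. There is a dedicated objective. SVC is summarised by visit and arm with change from baseline. Tracheostomy has Kaplan-Meier curves. Clinically significant SVC findings are recorded as adverse events, and pulmonary events fall within the primary safety endpoint. SAP 6.3 also says all data will be listed, so the ALSFRS-R items should be readable per person in Listing 16.2.9.1. All of this stands; what is missing is a summary score.

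**The placement is coherent.** The subscores sit under muscle function, and breathing has its own objective with a physiological measure. That is a defensible structure. It does not explain why the total loses the breathing items, nor does it describe the trend on its own scale.

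**The extension is a safety study.** The trend comes from an open-label, single-center study of 18 people, and confirming it is not a stated aim. Days 90 to 180 also belong to the parent study, whose documents are not available here. This stands and limits the weight of the point.

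**A corrected total would nearly suffice.** For participants with complete data, mean breathing change would equal total minus motor minus bulbar. This is true of the mean, but its SD and confidence limits could not be recovered from the table.

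**The VMALS-001 deaths.** Protocol 2.2.6.1 says "all deceased Participants died due to respiratory failure associated with ALS". This shows that respiratory decline matters clinically, but it does not decide which subscore to report, and mortality is already an endpoint.

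**Conclusion.** The point holds in a limited form. No ALSFRS-R breathing subscore is planned, and the SAP total contradicts the protocol's twelve-item score. As a result 12 of 48 points (25%) enter no summarised ALSFRS-R score, and the VMALS-001 breathing trend cannot be described on the scale where it was reported. These statements rest on item arithmetic and the documents' own definitions, with no outside assumption.

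A reader might also infer that the omission stops the extension from confirming or refuting the trend. That goes too far: with at most 18 participants and descriptive statistics only, the subscore would not settle the matter either. The standardised effects and interval widths in the working rest on an assumed effect and assumed SDs, and show scale only.

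Only exploratory endpoints are affected. The change is worth making because it is cheap, and because the discrepancy in the total needs resolving in any case.

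**What to change.** - Add breathing (items 10 to 12, range 0 to 12) as a third exploratory ALSFRS-R subscore in Protocol 1.1 and 3 and in SAP 3.2, 6.2.9 and 6.15.1, linked to the respiratory-function objective.
- Report its change from baseline at Days 240, 300 and 365 by arm in Table 14.6.1, in the same form as the other two subscores, and label it descriptive.
- Reconcile the total in SAP 6.2.9 with the twelve-item 0 to 48 score in Protocol 8.2.1, so that Table 14.6.1 and the slope figure use the same total. If a nine-item total is intended, SAP 9 should say so and give the reason.

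**Cost.** One derived variable and one table block from items already collected, plus a corrected derivation of the total. No new assessment is needed. The downside is one more exploratory summary; no formal test is planned for the ALSFRS-R, so there is no error rate to protect.
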